14.4.3 Secondary endpoint analysis

This study has not been powered for its secondary endpoints. The secondary analyses are for the purpose of hypothesis generation, rather than to provide firm conclusions. This study will inform the design of a future larger trial.

Means will be compared using the t-test (for normally-distributed continuous data), Mann-Whitney test (for non-normally-distributed continuous data), or Chi-square or Fisher's exact test as appropriate (for categorical data). Time-to-event data will be analysed and presented using Kaplan-Meier curves, the log rank test, and Cox proportional hazards regression.

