4.1.2 COPD exacerbation

The natural history of COPD is a gradual, progressive deterioration, punctuated by episodes of acute worsening, termed exacerbations. In a cohort of patients with severe COPD, the median exacerbation rate was 3 per year.⁶ Exacerbations often necessitate hospital admission—in 2004, COPD accounted for 111,077 emergency admissions to hospitals in the UK, and over one million hospital bed-days.⁷ Health-related quality of life is substantially worse in patients who have frequent exacerbations.⁶ Recovery from exacerbations is often slow,⁸ and the effect of treatment is modest.⁹ The 90-day mortality rate following hospitalisation for an exacerbation is 13.9%, and it is estimated that some 25% will have died within one year.⁴ In a study of male patients with previously stable COPD, those who were hospitalised for COPD exacerbation had a the 5-year mortality rate of 55.2%.¹⁰ By way of comparison, 5-year mortality rates for men with malignant melanoma, prostate cancer, and rectal cancer, were recently reported at 17.8%, 20.3% and 47.2%, respectively.¹¹ There is a clear need to develop new therapeutic strategies to improve management and outcomes of COPD exacerbations.

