Acute coronary syndrome	Clinical diagnosis of acute coronary syndrome by the treating physicians on the basis of typical symptoms and/or signs and/or results of investigations, and for which the patient is receiving treatment (likely to include aspirin, clopidogrel and low molecular weight heparin or fondaparinux, depending on local policy) at the time of screening
Hepatic insufficiency	Previous clinical, radiographic or histological diagnosis of liver cirrhosis, as reported by the patient or recorded in their hospital case notes; or a clinical suspicion of liver disease in conjunction with a serum bilirubin concentration >34 µmol/L
Excessive alcohol consumption	Patient-reported regular alcohol consumption of ≥56 units per week for men or ≥42 units per week for women, representing more than twice the UK recommended upper limits for sensible drinking
Malnourished or at high risk for malnutrition	Malnutrition Universal Screening Tool (MUST) ⁷⁰ score ≥2
Moribund or not for active treatment	Treating clinician and/or investigator judgement that the patient is unlikely to survive to hospital discharge, and/or the resulting discontinuation of treatments for the underlying condition
Admitted to critical care unit	Current admission of the patient to the any intensive care or high dependency unit, or a plan to do so imminently
Unable to give informed consent	
An investigator or physician judgement that the patient lacks the capacity to reach an informed decision on the appropriateness of their participation in the trial, due to an inability to:
 
 • understand the information relevant to the decision • retain that information • use or weigh that information as part of the process of making the decision, or • communicate that decision
Pregnancy or lactation	Patient-reported pregnancy or lactation, and/or a positive result from a urinary pregnancy test

8 Recruitment

Patient recruitment at a site will only commence once the trial team has ensured that the following approval/documents are in place:

- The REC and regulatory (MHRA) approvals
- A signed Clinical Trial Site Agreement (CTSA)
- Final sponsorship and host site approval
- The site/trial initiation visit has taken place

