11.4 Protocol Defined Events (PDEs)

This trial involves patients hospitalised for exacerbations of COPD, a condition that is associated with high morbidity and mortality. The in-hospital mortality rate has been reported to range between 4% and 30%. In an audit of a subset of patients with COPD (those who also had diabetes mellitus), 14/108 (13%) required non-invasive ventilation for respiratory failure, and 17/108 (16%) died in-hospital or within 30 days of discharge.

Many important and potentially Serious Adverse Events (SAEs) are common in the population under study, which are unlikely to be related to the IMP, but rather the underlying disease or co-morbidities and these will be identified and reported as Protocol Defined Events. A list of anticipated PDEs is presented below. The occurrence of any of the events listed below will be documented in the patients hospital notes, CRFs and Sponsor's AE Log. The PDEs will not be reported to Sponsor immediately using the SAE Reporting Form. However, the Sponsor will be made aware on regular review of the completed AE Log through submission to the JRO on request or every 2 months. Similarly, an assessment of expectedness will not be required unless they fall within the definition of an Adverse Reaction.

- Failure to recover to baseline
- Recurrent exacerbation of COPD
- Pneumonia
- Respiratory failure
- Sepsis

For the avoidance of doubt, a Protocol Defined Event remains as such even if it has an attribute that defines it at a Serious Adverse Event (for example, a recurrent exacerbation of COPD requiring hospital admission should be treated as a Protocol Defined Event).

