14.2.2 Secondary endpoints

Unless otherwise specified, the endpoints described below related to a comparison of data between the active treatment and placebo groups.

Clinical efficacy:

- COPD Assessment Test score at 4 weeks and, where available, at 12 weeks—defined as the sum of the points marked on the patient-completed COPD Assessment Test, as published; comparisons of mean score at follow-up and proportion of patients with improvement ≥ 5 points
- Exacerbation of Chronic Pulmonary Disease Tool (EXACT) scores—mean scores at days 5, 10 and 28
- time to medical fitness for discharge—defined as the number of days between study enrolment and the day on which the patient is documented by the clinical care team to be medically fit for hospital discharge, if this is different to the date of actual discharge
- time to actual discharge—defined as the number of days between study enrolment and the day on which the patient is discharged from the hospital
- rates of recurrent exacerbation, readmission, or death—defined, respectively as the number of days between study enrolment and the day on which the patient is prescribed a systemic antibiotic or steroid (for an exacerbation of COPD), is readmitted to hospital (for any reason except planned elective treatment or investigation), or dies (from any cause)

Glycaemic control:

- mean daily insulin use during hospitalisation period—defined as total number of units of insulin administered (of any formulation), divided by the duration of hospitalisation (in days)
- mean HbA1c and serum fructosamine concentration at follow-up, and change from baseline

Inflammation and infection:

- mean C-reactive protein concentration at discharge and follow-up (absolute values and change from baseline)
- a relevant panel of markers of inflammation and oxidative stress, measured on serum samples collected at study entry, discharge and follow-up (absolute values and change from baseline)

Other metabolic effects:

- mean body mass index at follow-up
- mean waist circumference at follow-up

Airflow limitation

- FEV₁ at 4 weeks—mean values at follow-up and mean change from discharge

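### The methods named for time to medical fitness and time to discharge make no provision for in-hospital death; if deaths are censored, the Kaplan-Meier curve modestly overstates discharge

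*Protocol*

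**What the plan says.** Section 14.4.3 gives one sentence for all such endpoints: "Time-to-event data will be analysed and presented using Kaplan-Meier curves, the log rank test, and Cox proportional hazards regression".

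Section 14.2.2 defines time to actual discharge as "the number of days between study enrolment and the day on which the patient is discharged from the hospital". Time to medical fitness runs from enrolment to "the day on which the patient is documented by the clinical care team to be medically fit for hospital discharge", where that differs from the date of actual discharge. Neither definition gives a value or a rule for a patient who dies first. No section sets a censoring rule or names death as a competing event, and section 14.4.5 plans no sensitivity analysis.

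The protocol foresees deaths before discharge. Section 11.4 states: "The in-hospital mortality rate has been reported to range between 4% and 30" per cent. The stopping criteria in section 9.10.2 provide for an enrolled patient who is not expected to survive the admission, and section 14.2.2 lists all-cause death as an endpoint.

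Section 14.4.3 declares the secondary analyses unpowered and hypothesis-generating. Section 5.2 adds that the secondary data will help to choose endpoints and to size a larger trial.

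**The concern.** Kaplan-Meier estimates the proportion with an event on the footing that a censored patient stays as likely to have it as those still under observation. That is reasonable for a patient lost to follow-up. It is not reasonable for one who has died in hospital, whose chance of discharge is zero. Censoring that patient at death redistributes the lost probability to the survivors, so the curve heads towards 100% discharged whatever the number of deaths.

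Two things are at stake. The first is the description: day-28 proportions and median times to discharge would look better than what happened, and section 5.2 intends such figures to feed the design of the next trial. The second is the comparison: with deaths censored, log rank and Cox ask only whether patients still alive in hospital leave at the same rate in each arm. An arm with more deaths could look no different on these endpoints.

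**Working it through.** The protocol states no figure for these endpoints, so there is nothing to reproduce. Its sample-size calculation concerns the glucose endpoint only and has no bearing here.

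**Inputs**
- Length of stay (section 6.4): median 9 days, interquartile range 5 to 17; a later audit gives a median of 8. These are stays of a wider population, used here as time from enrolment.
- In-hospital mortality p: 4%, the low end of the range in section 11.4, and 10%, which is an assumption. The protocol gives no expected value for this trial.
- Target sample size 69, allocated 2:1 (section 6.2). That is 46 and 23 if the ratio holds throughout; section 14.5 expects it only approximately.
- Assumption: deaths and discharges have the same timing distribution.

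**Within one group, constant hazards.** With median stay m, the total exit hazard is h = ln 2 / m. For m = 9, h = 0.0770 per day, and h × 28 = 2.1565.

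- Discharged by day t on Kaplan-Meier, deaths censored: 1 − exp(−h(1 − p)t)
- Truly discharged by day t (cumulative incidence): (1 − p)(1 − exp(−ht))

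At p = 4%: 1 − exp(−2.1565 × 0.96) = 87.4%, against 0.96 × (1 − exp(−2.1565)) = 84.9%. Excess 2.5 points.

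At p = 10%: 1 − exp(−2.1565 × 0.90) = 85.6%, against 0.90 × (1 − exp(−2.1565)) = 79.6%. Excess 6.1 points before rounding.

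**Sensitivity to the stay distribution, day 28**

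| Model | p = 4%: Kaplan-Meier vs true | p = 10%: Kaplan-Meier vs true |
|---|---|---|
| Constant hazard, median 9 | 87.4% vs 84.9% | 85.6% vs 79.6% |
| Constant hazard, median 8 | 90.3% vs 87.5% | 88.7% vs 82.0% |
| Log-normal, median 9, IQR 5 to 17 (simulated) | 88.6% vs 86.0% | 86.9% vs 80.6% |

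The excess is 2.5 to 2.7 points at 4% and 6.1 to 6.7 points at 10%. The median moves less: with m = 9, from 9.55 to 9.38 days at 4% and from 10.5 to 10.0 days at 10%. In 69 patients, 4% is 2.8 deaths and 10% is 6.9.

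**Between arms.** Give both arms the same discharge hazard d = ln 2 / 9, but let long-run in-hospital death be 4% in one and 10% in the other. The death hazard is then d × p/(1 − p), and the total hazard is d/(1 − p).

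- Cause-specific hazard ratio: 1. Kaplan-Meier at day 28 in both arms: 1 − exp(−2.1565) = 88.4%.
- True discharge at 4%: 0.96 × (1 − exp(−2.1565/0.96)) = 85.8%.
- True discharge at 10%: 0.90 × (1 − exp(−2.1565/0.90)) = 81.8%.

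The true gap of 4.0 points shows in neither the curves nor the hazard ratio. Such a gap could arise by chance: in a placebo arm of 23, one death is 1/23 = 4.3% and two are 8.7%.

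**The case against.** The strongest reply is that the protocol never says deaths are censored at death. It names a family of methods, and Kaplan-Meier, log rank and Cox can all be run with deaths kept at risk as never discharged, leaving section 14.4.3 as it stands. A separate SAP, not available here, may set that rule. This stands. A reader might infer that the protocol prescribes a wrong estimator, but the documents support only a conditional statement. It also does not say in words that the two discharge endpoints belong to the time-to-event class, though their names make any other reading unlikely.

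A reader might also infer that all three methods overstate discharge. They do not. With deaths censored, log rank and Cox validly compare cause-specific hazards, and the limit is what they leave out. Nor does any calculation here show that an arm with more deaths would look faster to discharge.

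Finally, a reader might apply the higher mortality figures and report a bias of 9 points or more. The documents do not support that for this trial. The 16% comes from an audit of COPD patients with diabetes, and it counts later deaths too: "17/108 (16%) died in-hospital or within 30 days of discharge". Section 7.2 excludes diabetes treated with insulin or oral agents. Both 16% and the upper end of 30% exceed the protocol's own longer-term figure in section 4.1.2: "The 90-day mortality rate following hospitalisation for an exacerbation is 13.9" per cent. Section 7.2 also excludes severe sepsis, decompensated respiratory failure, critical care admission, and patients for whom there is a "Treating clinician and/or investigator judgement that the patient is unlikely to survive to hospital discharge".

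At 4% mortality the excess is smaller than sampling error: the standard error of an 86% proportion is about 4 points with 69 patients (√(0.86 × 0.14/69) = 4.2%), and 5 and 7 points with 46 and 23. Similar mortality in both arms would largely cancel the excess in the contrast. Death is already a secondary endpoint, so deaths would not vanish from the report. These points make the matter minor. They do not remove the gain from settling it, because the right display costs almost nothing.

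**Conclusion.** The point holds as a minor, conditional one. The named methods come with no provision for death before discharge. If deaths are censored at death, the Kaplan-Meier curve overstates the proportion discharged by day 28 by about 2 to 3 points at 4% in-hospital mortality and about 6 points at an assumed 10%. Log rank and Cox would be sound as cause-specific comparisons, but blind to a difference in deaths between arms.

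The sizes rest on a median stay of 8 or 9 days, on deaths and discharges having similar timing, and on mortality values that the protocol does not give for its own selected population. The low end is the more plausible. The primary endpoint is untouched. What is affected is the reading of two exploratory endpoints and their use in planning the larger trial.

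**What to change.** In section 14.4.3, add a provision for time to medical fitness and time to discharge:

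- Present cumulative incidence curves by arm, with in-hospital death as a competing event. Equivalently, keep patients who die in hospital at risk as never discharged to the end of a fixed window, stated in advance (day 28 would match the calculation above). The two agree exactly when nobody is otherwise censored before the window ends.
- If a Cox model or log rank test with deaths censored is kept, label it as a comparison of cause-specific discharge hazards. Gray's test or a Fine-Gray model may be added.
- Show the number of in-hospital deaths by arm beside these results.

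The cost is a few sentences, a little more analysis work and a display less familiar to clinical readers. Trial conduct, data collection and sample size do not change.

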14.4.4 Sub-group analyses

A single subgroup analysis is planned, based on the presence or absence of radiographic consolidation on the admission chest radiograph. The presence of radiographic consolidation shall be defined as a report by a radiology specialist of definite or likely consolidation or airspace shadowing on the first chest radiograph obtained during the hospitalisation period, which was not present on previous chest radiographs (if available), and for which pneumonia is a differential diagnosis. Where no chest radiograph has been performed, it shall be assumed that consolidation is absent (it is considered extremely unlikely that a patient admitted for COPD would not have a chest radiograph performed at or soon after admission).

The presence of radiographic consolidation is thought to identify patients with a different clinical phenotype and prognosis. As such, the primary and secondary analyses will be repeated in those patients who do, and do not, have evidence of radiographic consolidation. These will be considered as secondary endpoints and regarded as hypothesis-generating.

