14.3 Sample size and recruitment

14.3.1 Sample size calculation

In an audit and service evaluation study conducted in this centre (unpublished data, available from PI), the case notes of 20 patients hospitalised for COPD exacerbations were evaluated retrospectively. A median of 2 capillary glucose measurements were made per patient (interquartile range 1.8–3.3). The measurements had a mean value of 7.7 mmol/L and standard deviation 1.5 mmol/L. Based upon these data, a sample size of 44 (randomised equally to treatment and control groups) would allow the detection of a difference in the mean glucose concentrations between the two groups of 1.5 mmol/L with 90% power (using the *t*-distribution with a two-sided alpha of 0.05). This difference would be clinically significant and, on the basis of prior observational data,¹⁴ might correspond to a difference in the risk of adverse outcome (death or prolonged hospitalisation) of 22.5%. In the initial calculation of sample size, provision was made for an expected drop-out rate of approximately 5%, resulting in a target recruitment size of 46 patients. With effect from Substantial Amendment 4 approval, the target sample size is increased to 69 patients, with a change in the active:placebo allocation ratio from 1:1 to 2:1 (maintaining stability of the control group size). This is to permit a fuller assessment of the feasibility, safety and tolerability of the drug when used in COPD exacerbations in accordance with the accelerated dose-escalation regimen. Under conditions of 2:1 allocation, the minimum number of participants required to maintain statistical power for the primary endpoint analysis (as defined above) is 48.

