14.4 Statistical analysis plan

14.4.1 Summary of baseline data and flow of patients

The report will detail the number of eligible patients for the trial, the number consenting and the number randomised. A breakdown will be presented for each group of the numbers of participants assigned, receiving the intended treatment, completing the study protocol, and analysed for the primary outcome. This information will be displayed as a flow diagram.

The following data will be used to describe baseline comparability of study groups:

- Age (continuous)—mean and standard deviation

- Sex (categorical)—proportions
- COPD Assessment Test score (interval scale)—mean and standard deviation
- Exacerbation of Chronic Pulmonary Disease Tool score (interval scale)—mean and standard deviation
- Forced expiratory volume in 1 second (continuous)—mean and standard deviation
- Presence of radiographic consolidation (categorical, defined by the presence or absence of consolidation or airspace shadowing on a chest X-ray, as reported by a radiology specialist as part of routine clinical practice)—proportions
- Venous blood glucose concentration (continuous)—mean and standard deviation
- Haemoglobin A1c (continuous)—mean and standard deviation
- C-reactive protein concentration (continuous)—mean and standard deviation

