14.4.2 Primary endpoint analysis

The primary analysis will be performed in accordance with the intention to treat principle. For comparison, a per protocol analysis will be provided as a secondary outcome measure. Statistical significance shall be defined as a two-sided p-value <0.05. Any post hoc analyses will be defined as such in the research report. No interim analyses are planned.

The primary endpoint for this study will be the mean hospitalisation glucose concentration. The mean of the individual mean values recorded among participants allocated to active treatment will be compared with the mean of the individual mean values recorded among patients allocated to placebo treatment. The significance of the observed difference will be tested using an independent sample t-test.

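### The consolidation subgroup plan analyses each stratum separately and never compares the two treatment effects, so it cannot show whether the effect differs between them

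*Protocol*

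**What the plan says.** Protocol section 14.4.4 prespecifies one subgroup factor: "A single subgroup analysis is planned, based on the presence or absence of radiographic consolidation on the admission chest radiograph". The reason given is that consolidation is thought to mark a clinically distinct group with a different outlook. The method is that "the primary and secondary analyses will be repeated in those patients who do, and do not, have evidence of radiographic consolidation". On status, the section adds: "These will be considered as secondary endpoints and regarded as hypothesis-generating".

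The analysis repeated for the primary endpoint is the one in section 14.4.2: "The significance of the observed difference will be tested using an independent sample t-test". The threshold there is: "Statistical significance shall be defined as a two-sided p-value <0.05". Section 14.4.5 plans no further analyses. The protocol contains no interaction term and no other contrast between the two strata.

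Consolidation is described twice. For the baseline table, section 14.4.1 has it "defined by the presence or absence of consolidation or airspace shadowing on a chest X-ray". Section 14.4.4 asks for more. The radiology report must call it definite or likely, "on the first chest radiograph obtained during the hospitalisation period"; it must be absent from earlier films where these exist; and pneumonia must be among the possible diagnoses. A patient with no film counts as negative.

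**The concern.** The stated reason for the subgroup is that the two groups may differ, but the method only asks, twice, whether metformin differs from placebo. A significant result in one stratum and a non-significant one in the other is not evidence that the effects differ, because the strata also differ in size and hence in power. A difference in prognosis does not imply a difference in treatment effect either. Only an estimate of the difference between the two effects addresses that, and none is planned.

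At stake is the use made of these results. Section 14.4.3 says the study will inform a larger trial. A contrast produced by stratum size alone could be carried into that design.

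The two definitions add a smaller problem. A patient with old, unchanged shadowing is positive in the baseline table and negative in the subgroup analysis, so the two sets of counts need not agree.

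**Working it through.** **Inputs from the protocol.** Section 14.3.1 gives a difference of 1.5 mmol/L, SD 1.5 mmol/L, 90% power, a "two-sided alpha of 0.05", and 69 patients at 2:1, taken here as 46 metformin and 23 placebo. Section 14.5 says the final ratio is only approximately 2:1.

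**Assumption.** The prevalence of consolidation is not given, so a range is shown, with the same prevalence in both arms.

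**Formula.** For n1 and n2 patients, the standard error is SE = 1.5 × √(1/n1 + 1/n2). Power is the probability that a noncentral t variable with n1 + n2 − 2 degrees of freedom and noncentrality 1.5/SE falls outside the two-sided 5% limits.

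**The plan's own figures.**
- 22 + 22 gives 90.0%, which reproduces the 44 patients.
- 32 + 16 gives 89.2%, close to the stated minimum of 48 at 2:1.
- 46 + 23 gives 97.1% overall.

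**Worked case, 25% prevalence, identical effect in both strata.**
- With consolidation (12 metformin, 6 placebo): SE = 1.5 × √(1/12 + 1/6) = 0.75. Noncentrality is 1.5/0.75 = 2.0 on 16 df, and power is 46.8%.
- Without consolidation (34, 17): SE = 1.5 × √(1/34 + 1/17) = 0.446. Noncentrality is 3.37 on 49 df, and power is 91.0%.
- The strata share no patients, so the tests are independent. P(exactly one significant) = 0.468 × 0.090 + 0.910 × 0.532 = 0.53. Rounding 11.5 metformin patients down to 11 instead gives 0.54.

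**Interaction, same case.** The SE of the difference between the two effects is √(0.75² + 0.446²) = 0.87. Its 95% CI extends about 2.0 × 0.87 = 1.7 mmol/L either side. Power to detect a 1.5 mmol/L difference in effect, on 65 df, is 40%.

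**Across the assumed range** (true effect 1.5 mmol/L in both strata; sizes are metformin:placebo):

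| Prevalence | With | Without | Power with | Power without | Exactly one significant | Interaction power for a 1.5 difference |
|---|---|---|---|---|---|---|
| 10% | 5:2 | 41:21 | 16% | 96% | 81% | 20% |
| 15% | 7:3 | 39:20 | 25% | 95% | 72% | 26% |
| 20% | 9:5 | 37:18 | 38% | 93% | 60% | 35% |
| 25% | 12:6 | 34:17 | 47% | 91% | 53% | 40% |
| 30% | 14:7 | 32:16 | 54% | 89% | 47% | 43% |
| 40% | 18:9 | 28:14 | 65% | 85% | 39% | 47% |
| 50% | 23:12 | 23:11 | 78% | 75% | 36% | 49% |

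**Other true effects.**
- A uniform 1.0 mmol/L gives 62% at 15% prevalence and 49% at 50%.
- No effect gives 2 × 0.05 × 0.95 = 9.5% per endpoint at any prevalence.

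In simulation (20,000 trials per scenario), the interaction test rejected in 4.7% to 5.4% of trials when the two effects were equal.

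**The case against.** The case for leaving the text alone has real weight. There is one prespecified factor, the results are labelled hypothesis-generating, and section 14.4.3 disclaims firm conclusions from secondary analyses. The protocol nowhere says it will compare p-values between strata or claim that the effect differs. An interaction test in 69 patients would miss a true 1.5 mmol/L difference in effect at least half the time, so the gain is mainly in how results are presented. An SAP that is not at hand could add such an estimate.

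Most of this stands, and it limits the severity. It does not repair the method. The protocol itself fixes the separate analyses and offers no other way to compare the strata, and a label does not make a contrast driven by stratum size a sound hypothesis. Low power for interaction is a reason to show the estimate with its interval.

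Four stronger readings are tempting, and the documents do not support them:
- *That the plan will produce a false subgroup claim.* The error arises only if someone compares significance across the strata, and the high rates need a true effect.
- *That the smaller stratum will usually be non-significant.* At 30% and 40% prevalence its power is 54% and 65%, so it would more often be significant.
- *That this subgroup will set the next trial's population.* Section 5.2 names endpoint selection and sample size, and section 14.4.3 speaks only of design. Restriction of the population is a reader's inference.
- *That the qualifying film may well follow randomisation.* Section 14.4.4 specifies the admission radiograph and expects it at or soon after admission; section 6.2 allows entry up to 48 hours after admission. A later film is possible but marginal.

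**Conclusion.** The point holds as a flaw of method in an exploratory analysis. Section 14.4.4 cannot show whether the treatment effect depends on consolidation. If the design effect is present equally in both strata, one would be significant and the other not in about 36% to 72% of trials, for prevalence from 50% down to 15%, against 5% for an interaction test. If there is no effect, the rate is about 9.5% per endpoint, against 5%. These figures rest on the protocol's difference and SD, on 46:23 allocation with all 69 patients analysed, and on an assumed prevalence. The primary conclusion is not touched. The mismatch between the two definitions of consolidation follows from the text without any assumption and is minor.

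**What to change.** Reword section 14.4.4 as follows:
- For the primary endpoint, fit a linear model with treatment, consolidation and their interaction, and report the interaction estimate with its 95% CI.
- Show the treatment effect in each stratum with a 95% CI and no within-stratum p-value.
- Do the same for at most a short, named list of secondary endpoints, in place of repeating every analysis.
- State that power for interaction is low: roughly 20% to 49% for a 1.5 mmol/L difference in effect, at prevalences from 10% to 50%.
- Use the section 14.4.4 definition of consolidation, based on the admission radiograph, in the section 14.4.1 baseline table too.

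The primary analysis is a t-test, so there is no existing model to extend. The linear model is an addition for the subgroup question, and the t-test can stay as it is. The cost is protocol wording, with any matching SAP text, and one extra model. No new patients or data are needed. Section 14.7 requires substantive changes made after the analysis plan is finalised to be reported and justified. What is given up is a p-value in each stratum; what replaces it will be imprecise, with an interval of about ±1.7 mmol/L at 25% prevalence, and should be described as such.
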